204 on a standard Android smartphone and uses Bluetooth (BT) to communicate with a CGM and Near
205 Field Communication (NFC) to communicate with insulin pens. Currently, inControl runs on a
206 modified release of the Android operating system (OS). Modifications of the OS include the removal
207 of unnecessary applications and functions, and fixes to the BT stack to permit communication with
208 peripheral medical devices. The local inControl module is an Android application with a JS/CSS UI.
209

•

210 inControl-AP: When running closed-loop control, inControl-AP communicates with an insulin pump
211 and modulates insulin delivery automatically to keep blood glucose in a target range. inControl-AP
212 operates on a 5-minute cycle based on the highest frequency of input data. There are three insulin
213 dosing modes (stopped, pump and closed loop) and three operating modes (normal, sleep and

214 exercise). The combination of insulin dosing mode and operating mode determines what actions
215 inControl-AP will perform and what options are presented to the user.

216 inControl-Cloud is an external server system that communicates with the Network Service within
217 inControl-AP over a secure SSL to:

218 • Allow the patient to log in with their inControl-Cloud ID;
219 • Deliver user biometric data (height, weight, date of birth etc.) and therapy profile information
220 (basal rate, carbohydrate to insulin ratio, correction factor).

221 inControl Advice: In this protocol, we now intend to use inControl-Advice, which is designed to
222 provide advice to users, instead of directly controlling the insulin delivery system. inControl Advice
223 shares many of the features of inControl-AP described above, but does not implement automated
224 insulin delivery and receives data from an insulin pen. Instead of automated 5-min adjustments to the
225 insulin delivery, the system provides a series of real-time alerts and on-demand advice, for both dosing
226 of insulin and ingestion of carbohydrates, based on data collected from T1DM patients (i.e.
227 carbohydrate consumption, insulin injected, CGM) and inControl Cloud analytics. inControl Advice
228 includes 6 modules:

229 1. Retrospective analysis of the past few weeks, based on replay simulation technologies which
230 optimizes the patient's functional insulin therapy parameters (basal doses, insulin sensitivity
231 (ISF) factors, and carbohydrate ratios);

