232 2. A CGM-based bolus calculator that enhances usual computations ($\text{bolus} = \text{CHO/CR} + (\text{SMBG-}$
233 target)/ISF - IOB) by replacing the SMBG value with a short term (30 minutes) glucose
234 prediction;
235 3. A Hypoglycemia alert system capable of predicting hypoglycemic events within the next 3
236 hours;
237 4. A long-term tracker of average glycemia using CGM to estimate changes in HbA1c;
238 5. A nighttime adviser, minimizing the risk of overnight exposure to hypoglycemia by proposing
239 adequate bedtime carbohydrate intake which is optimized to minimize the exposure to
240 hyperglycemia;
241 6. A physical activity adviser, allowing for safe physical activity without hypoglycemia and
242 without increasing the risk of rebound hyperglycemia.

243 The feasibility and safety of a prototype DSS is currently being tested in 30 adults with T1DM, both
 244 insulin pump and MDI users. This single-site clinical trial follows a non-blinded randomized crossover
 245 design, with two 48-hour
 246 observation periods where
 247 patients are exposed to a
 248 variety of meal and physical
 249 activities to challenge the
 250 patients' own control
 251 strategies and the advisory
 252 system. Preliminary analysis
 253 of the first 11 patients
 254 showed a clear trend towards
 255 increased time spent in good
 256 control (between 70-
 257 180mg/dL, which was
 258 associated with a reduction in
 259 both hyperglycemia and
 260 hypoglycemia exposure (See
 261 Figure 3). The effect size was
 262 above 0.5. Use of the
 263 decision support system also
 264 reduced glucose variability,
 265 as shown by the Low BG
 266 Index [13] and by the
 267 Average Daily Risk Range
 268 [14], with effect size of 0.4.
 269 Our previous decision-
 270 support trial [7] and these preliminary data were used in the power calculations for this study.
 271

[figure not shown]

Figure 3: Results from pilot-feasibility testing of Decision Support System

272 1.3 Synopsis of Study Protocol

273 1.3.1 Study Objective

274 The objective of the study is to assess the efficacy of CGM+DSS versus CGM alone to improve
 275 glucose control in T1DM patients using multiple daily injections (MDI). The system will be deployed
 276 on a portable medical application platform (inControl Advice) and will include the following elements:

- 277 1. An MDI treatment parameters optimization routine, using a month of collected Continuous
 278 Glucose Monitoring (CGM)/insulin/meal data

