349 possible exception of additional phone contacts based on DSS-requested optimization of insulin
350 parameters for the CGM+DSS group.

- 351 • Phone contacts after: 2 weeks, 4 weeks, 6 weeks, 8 weeks, and 10 weeks for collection of CGM
352 downloads
- 353 • Alternately, emails may be used to contact study subjects.

354
355 The Study Conclusion will be a clinic visit for central HbA1c and post-intervention questionnaires.
356

358 **Figure 4: Study Flow Diagram**

359

360

361 **Table 1: Schedule of Study Visits/Phone Contacts and Examination Procedures During 12 week**
 362 **RCT Phase (Randomization at Week 0)**

	Pre	0	2w	4w	6w	8w	10w	12w
Visit or Phone	V	V	P	P	P	P	P	V, P
Comment	Screen/Enroll, Blinded CGM run-in	Rand						Conc
Eligibility Assessment	X	X						
Blinded CGM (2 weeks)	X							
HbA1c (Central lab)	X							X
Blood draw for screening labs (chemistry panel, liver function tests, and TSH)	X							
Urine or serum pregnancy test (premenopausal females not surgically sterile)	X	X						
CGM Data download		X	X	X	X	X	X	X
Assessment for BGs <50 or >300 and AEs		X	X	X	X	X	X	X
Clarke Hypoglycemia Awareness Scale, Hyperglycemia Avoidance Scale, Fear of Hypoglycemia Survey, Diabetes Distress Scale, Diabetes Specific Personality Questionnaire, and Technology Expectations Survey (CGM+DSS group)		X						
Clarke Hypoglycemia Awareness Scale, Hyperglycemia Avoidance Scale, Fear of Hypoglycemia Survey, Diabetes Distress Scale, and Technology Acceptance Survey (CGM+DSS group)								X

363

364 **1.3.7 Endpoints**

365 *Primary Efficacy Outcome:*

366 The primary efficacy outcome is increased % time within target range defined as CGM readings of 70-
367 180 mg/dL during the day and 80-140 mg/dL overnight.

368

369 *Secondary Efficacy Endpoints:*

370 Secondary efficacy endpoints include

371 1. Optimized metabolic control for the entire study population defined as:

372 a. Reduced risk for hypoglycemia, and

373 b. Reduced postprandial blood glucose variability defined by the postprandial High Blood
374 Glucose Index and by area under the postprandial CGM glucose curve;

375 2. Selective improvements for specific sub-populations defined as follows:

376 a. Reduced HbA1c without increasing risk for hypoglycemia (measured by the Low Blood
377 Glucose Index), particularly for those who were poorly controlled at the baseline
378 (baseline A1c > 8%);

379 b. Reduced incidence and risk for hypoglycemia without deterioration in HbA1c for those

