426 To be eligible for the pilot and main study, a subject must meet the following criteria:

1. Willingness to provide informed consent
2. Clinical diagnosis, based on investigator assessment, of type 1 diabetes for at least one year and using insulin for at least 1 year
3. Using basal and meal insulin (NovoLog® [insulin aspart], Humalog® [insulin lispro] or Apidra® [insulin glulisine]) for Intensive Insulin Therapy including carbohydrate counting and use of pre-defined parameters for glucose goal, carbohydrate ratio, and insulin sensitivity factor for at least 1 months.
4. Age ≥ 15.0 years old
5. Willingness to use the study basal insulin (Tresiba® [insulin degludec]) and meal insulin (NovoLog® [insulin aspart]) for the duration of the study.
6. Willingness to use the home or DSS-optimized carbohydrate counting parameters for all meal dosing and enter the information into the inControl APP (for CGM+DSS group).
7. For females, not currently known to be pregnant
8. If female and sexually active, must agree to use a highly effective form of contraception to prevent pregnancy while a participant in the study. A negative serum or urine pregnancy test will be required for all premenopausal women who are not surgically sterile. Subjects who become pregnant will be discontinued from the study. Also, subjects who during the study develop and express the intention to become pregnant within the timespan of the study will be discontinued.
9. Ability to access the Internet to provide data to the clinical team or to travel to the research center so that the study equipment can be downloaded.
10. Ability to have 3G or Wi-Fi to be able to use the DSS smart bolus calculator and advice given (i.e. sleep, exercise).
11. Demonstration of proper mental status and cognition for the study
12. Investigator has confidence that the subject can successfully operate all study devices and is capable of adhering to the protocol
13. If on a non-insulin hyperglycemic therapy, stability on that therapy for the prior 3 months and willingness not to alter the therapy for the study duration.

455

456 **2.2.2 Exclusion**

457 The presence of any of the following is an exclusion for the study:

1. Medical need for chronic acetaminophen

459 2. Use of any medication that at the discretion of the clinical protocol chair is deemed to
460 interfere with the trial.

461 3. Current treatment of a seizure disorder.

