759 Subjects in both groups will be provided with the software needed to download the study CGM
760 and transmit the data to study personnel and will be asked to do so prior to scheduled phone
761 contacts for the remainder of the study.

762 **5.2 Procedures for the CGM+DSS Group**

763 **5.2.1 DSS Training**

764 Subjects randomized to the CGM+DSS group will receive DSS training.

765 The subject will be trained by qualified study staff to use the DSS (inControl Advice) APP to
766 calculate insulin doses for meals and corrections. Prior to initial use, the inControl system will be
767 initialized by a study team member with each subject's individual insulin dosing parameters,
768 including carbohydrate ratio, insulin sensitivity factor and basal insulin dose.

769 Study team members will train the subject in performing specific tasks including the following:

- 770 • The study team will confirm the carbohydrate counting parameters entered in the system
771 with the study physician.
- 772 • How to activate the "meal" screen of the inControl system any time insulin will be given
773 with a meal and the "add correction" screen any time additional correction insulin is
774 desired
- 775 • How to use the NFC communication on the insulin pens to inform and confirm on the
776 inControl system that an insulin dose was injected.
- 777 • How to inform the system of hypoglycemia treatment via a "hypoglycemia treatment"
778 button on the inControl user interface after glucose is consumed that is not accompanied
779 by an insulin bolus
- 780 • What to do when exercising while using the system and how to react to the exercise
781 advice given
- 782 • How to react to the hypoglycemia risk alarm.
- 783 • How to access the bedtime button and react to the possible advice for a bedtime snack.

784 The subject will also be instructed to contact study staff during periods of illness with an
785 elevated temperature >101.5 degrees Fahrenheit (38.6 degrees Celsius), periods of significant
786 illness, or during periods of use of medications such as epinephrine (e.g. for the emergency
787 treatment of a severe allergic reaction or asthma attack) or oral or injectable glucocorticoids to
788 determine if study procedures should be temporarily discontinued.

789 Subjects will be given the inControl Advice device and will be provided with sufficient supplies
790 to last until the final clinic visit.

791 **5.3 Procedures for the CGM Group**

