930 **7.1.2 Safety Measures**

931

932 **7.1.2.1 Hypoglycemia Safety Protocol**

933 All subjects will be required to set the CGM hypoglycemia threshold alarm to a value no less than 70
934 mg/dL.

935

936 If a subject receives a CGM hypoglycemia threshold alarm or notes that the CGM glucose is <70
937 mg/dL, confirmatory fingerstick testing will be recommended and the subject will be instructed to treat
938 hypoglycemia with ~16 grams of fast-acting oral glucose.

939

940 **7.1.2.2 Hyperglycemia Safety Protocol**

941 Subjects will be required to set the CGM hyperglycemia threshold alarm to a value no greater than 300
942 mg/dL.

943

944 If a subject receives a CGM hyperglycemia threshold alarm or notes that the CGM glucose is ≥ 300
945 mg/dL, confirmatory fingerstick testing will be recommended.

946

947 If a subject's CGM reading is ≥ 300 mg/dL for over 1 hour, or ≥ 400 mg/dL at any point, the subject
948 will be instructed to take the following steps:

949

950 • Perform a blood ketone measurement with the study ketone meter. Subjects will also be
951 encouraged to check ketones if they are clinically concerned.

952 • Correction insulin may be taken per the subject's usual routine (CGM group) or per the
953 inControl Advice recommendation (CGM+DSS group).

954 • Subjects will be instructed to administer correction insulin per the subject's usual routine
955 (CGM group) or per the inControl Advice recommendation (CGM+DSS group) for ketones
956 ≥ 0.6 mmol/L and to additionally notify study staff for ketones ≥ 3.0 mmol/L.

957

958 **7.1.2.3 Study System Failure**

959 If the inControl Advice APP stops working, subjects will be instructed to resume their regular home
960 insulin therapy until he/she can contact study staff for confirmation of the current carbohydrate
counting parameters or until the study system can be repaired or replaced.

961 **8 ADVERSE EVENTS, DEVICE ISSUES, POTENTIAL RISKS, AND STOPPING RULES**

962 **8.1 Adverse Event Definition**

963 A reportable adverse event for this protocol includes any untoward medical occurrence that meets
964 criteria for a serious adverse event or any unanticipated medical occurrence in a study subject that is
965 study- or device-related, including severe hypoglycemia as defined below and severe
966 hyperglycemia/diabetic ketoacidosis (DKA) as defined below. Skin reactions from sensor placement
967 are only reportable if severe and/or required treatment.

968

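### The app-failure rule sends CGM+DSS subjects back to home insulin therapy without saying that study insulins continue or which basal dose applies

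*Combined protocol and SAP*

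**What the plan says.** Section 7.1.2.3 reads: "If the inControl Advice APP stops working, subjects will be instructed to resume their regular home" "insulin therapy until he/she can contact study staff for confirmation of the current carbohydrate" counting parameters, or until the system is repaired or replaced. It names no insulin product and no basal dose.

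Other sections bear on how that sentence would be read:

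- **Insulin products.** Section 5.1 moves all subjects to degludec and aspart at randomization and keeps them on the study pens until the study ends. Eligibility criterion 5 in section 2.2.1 requires willingness to do so.
- **Return to home insulins.** Section 5.4.2 describes this switch at the conclusion visit, with physician review and doses given. It warns of possible severe hypoglycemia or hyperglycemia and asks for fingersticks before meals, at bedtime and at 3 AM for 3 days. Section 5.5 adds a safety call within 3 to 7 days.
- **Parameters.** Criterion 6 in section 2.2.1 treats home and DSS values as distinct sets: "Willingness to use the home or DSS-optimized carbohydrate counting parameters for all meal dosing". Section 5.2.1 loads the app with each subject's own values, "including carbohydrate ratio, insulin sensitivity factor and basal insulin dose". Section 1.2 says the retrospective module optimizes "functional insulin therapy parameters (basal doses, insulin sensitivity" factors and carbohydrate ratios). Section 1.3.1 lists the same element: "An MDI treatment parameters optimization routine, using a month of collected Continuous". Section 1.3.6 foresees changes during the trial in the CGM+DSS group, through the "possible exception of additional phone contacts based on DSS-requested optimization of insulin" parameters.

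**The concern.** This is a working insulin-dosing instruction for the experimental arm. It applies when the dosing tool has failed and before staff have been reached, so the subject has only its wording to act on. Two things are unclear.

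First, the instruction does not say that the study insulins continue. Elsewhere the protocol uses the word home for the pre-study products. A subject who carried that usage over could go back to the old basal insulin without any of the precautions the protocol attaches to that switch.

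Second, the basal dose is left open. The rule has staff confirm only carbohydrate counting parameters, while the DSS works on basal dose, sensitivity factor and carbohydrate ratio together. A subject could therefore combine home ratios with a basal dose that has since been changed, a pairing that nobody has reviewed as a set.

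What is at stake is the safety of a few subjects over short periods. The estimate of treatment effect is not at issue.

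**Working it through.** No formula applies, and the plan states no figure to reproduce. The check is to set the sections side by side.

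**1. What home means.** The protocol uses the word in two ways. For products, the home insulins are the pre-study insulins: in the run-in (sections 1.3.6 and 4.1), at the switch to study insulins (5.1) and at the switch back (5.4.2). For parameters, the home values are the pre-defined ratios that the CGM-alone group doses from throughout (1.3.6) and that criterion 6 contrasts with DSS-optimized ones. Section 7.1.2.3 speaks of home insulin therapy, which covers either use or both, and does not say which.

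**2. Product.** On the product reading, section 7.1.2.3 contradicts section 5.1. It would also produce the switch that sections 5.4.2 and 5.5 surround with precautions, and it triggers none of them: no dosing instructions from a physician, no 3-day fingerstick schedule, no follow-up call. On the parameter reading there is no contradiction. Section 7.1.2.3 does not refer to section 5.1, so the reader has to choose.

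**3. Basal dose.** Section 5.1 settles that the study pens continue, but not at what dose. The starting degludec dose equals the previous total daily long-acting dose, so home and current basal doses first agree in units and can diverge once the dose is changed. Sections 1.2 and 5.2.1 show that the DSS holds the basal dose and can optimize it. Section 7.1.2.3 asks staff to confirm carbohydrate counting parameters only. No section in the available text states the basal dose to take during an outage.

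**4. Whether the parameters match.** The sentence itself separates home therapy from current parameters, so it allows that the two may differ. A complete home set is the regimen the control arm follows, and section 4.1.1 has it reviewed before randomization if glucose fell below 50 or rose above 300 mg/dL. That supports a home set used whole. It says nothing for home ratios used with a changed basal dose.

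**5. How the fallback ends.** It ends on staff confirmation or on repair or replacement. Subjects are not expressly told to call promptly.

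**6. Size.** The documents give no app-failure rate, no outage duration and no size or direction of DSS-driven changes. They also describe the optimizer's data window differently: a month in section 1.3.1, the past few weeks in section 1.2. The number of subjects affected, the dose error and the weeks at risk therefore cannot be computed.

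**The case against.** The strongest reply is that the rest of the protocol already settles the matter. Section 5.1 and criterion 5 keep subjects on study insulins and make no exception for app failure. The point at which the fallback ends, confirmation of carbohydrate counting parameters, concerns dose calculation and not product. What an outage removes is the meal and correction calculator ("A CGM-based bolus calculator that enhances usual computations"). Degludec is taken once daily and is not calculated at each injection, so loss of the app does not in itself alter it. Section 1.3.6 links optimization to phone contacts, so staff should know of changes, and subjects have staff contact details. CGM alarms, confirmatory fingersticks and ketone testing (7.1.2) and the glucagon kit (4.1) stay in place. Returning to familiar parameters when investigational software fails is also a defensible default.

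Most of this stands. It makes a product switch unlikely and any mixed period short. A reader might infer that the protocol instructs subjects to go back to their pre-study basal insulin; the documents do not support that, given section 5.1 and criterion 5. A reader might also try to put the harm in units of insulin. That would need an assumed meal, ratio and percentage change. Varying the carbohydrate ratio alone would only compare the home ratio with the DSS ratio, which is not the mixed-set risk.

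What the reply does not supply is a stated basal dose, or any text in section 7.1.2.3 that tells a subject in an outage which meaning of home applies.

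**Conclusion.** The point holds as a wording defect in a safety instruction. Read literally, section 7.1.2.3 conflicts with section 5.1 and with the supervised switch-back in sections 5.4.2 and 5.5, and it leaves the basal dose unstated although the DSS may have changed it. The likely intent is temporary manual dosing on the study insulins.

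The risk is limited and short-lived, and its size cannot be derived from the documents. A reader might infer that the gap threatens the trial's conclusions. It does not: power, error rates and the primary analysis do not depend on this sentence.

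Confidence is medium. The available text shows no body for section 8.4 (Device Issues), and the DSS training materials are not among the documents. Either may hold further failure handling, and its absence here is not counted against the plan. The conclusion rests on the sentence as it stands in section 7.1.2.3.

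**What to change.** Replace the sentence in section 7.1.2.3 with:

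> If the app stops working, subjects continue study degludec at the current prescribed dose and study aspart by study pen, calculate meal and correction doses manually from the most recent staff-confirmed written parameters (basal dose, carbohydrate ratio, sensitivity factor and glucose goal as one matched set), and contact study staff promptly.

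Give each CGM+DSS subject that written set at randomization and again at each staff-confirmed change, and put the same instruction in the DSS training.

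The cost is one sentence in the protocol and the training script, plus minor staff time to keep the written set current. It needs no extra visits or subjects and no change to the analysis.

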8.4 Device Issues

1064

1065

1066

1067

1068

1069

8.5 Potential Risks and Side Effects

1070

Loss of confidentiality is a potential risk; however, data are handled to minimize this risk.

1071

Hyperglycemia and ketone formation and hypoglycemia are always a risk in subjects with type 1 diabetes and subjects will be closely monitored for this. When wearing sensors and insulin infusion

1073 sets there is always a risk of skin rashes, allergic reactions to the tape, or infections at the insertion site.
1074 There is always a risk for a small piece of a sensor remaining under the skin or a sensor or infusion set
1075 breaking off under the skin.

1076

1077 **8.5.1 Venipuncture Risks**

1078 A hollow needle/plastic tube will be placed in the arm for taking blood samples. Blood draws can
1079 cause some common reactions like pain, bruising, or redness at the sampling site. Less common
1080 reactions include bleeding from the sampling site, formation of a small blood clot or swelling of the
1081 vein and surrounding tissues, and fainting.

1082

1083 **8.5.2 Fingerstick Risks**

1084 About 1 drop of blood will be removed by fingerstick for measuring blood sugars and sometimes
1085 HbA1c or other tests. This is a standard method used to obtain blood for routine hospital laboratory
1086 tests. Pain is common at the time of lancing. In about 1 in 10 cases, a small amount of bleeding under
1087 the skin will produce a bruise. A small scar may persist for several weeks. The risk of local infection
1088 is less than 1 in 1000. This should not be a significant contributor to risks in this study as fingersticks
1089 are part of the usual care for people with diabetes.

1090

1091 **8.5.3 Subcutaneous Catheter Risks (CGM)**

1092 Subjects using the CGM will be at low risk for developing a local skin infection at the site of the
1093 sensor needle placement. If a catheter is left under the skin for more than 24 hours it is possible to get
1094 an infection where it goes into the skin, with swelling, redness and pain. There may be bleeding where
1095 the catheter is put in and bleeding under the skin causes a bruise (1 in 10 risk).

1096

1097 Study staff should verbally alert the subject that on rare occasions, the CGM may break and leave a small
1098 portion of the sensor under the skin that may cause redness, swelling or pain at the insertion site. The
1099 subject should be further instructed to notify the study coordinator immediately if this occurs.

1100

1101 **8.5.4 Risk of Hypoglycemia**

1102 As with any person having type 1 diabetes and using insulin, there is always a risk of having a low
1103 blood sugar (hypoglycemia). The frequency of hypoglycemia should be no more and possibly less
1104 than it would be as part of daily living. Symptoms of hypoglycemia can include sweating, jitteriness,
1105 and not feeling well. Just as at home, there is the possibility of fainting or seizures (convulsions) and
1106 that for a few days the subject may not be as aware of symptoms of hypoglycemia. A CGM
1107 functioning poorly and significantly over-reading glucose values could lead to inappropriate insulin
1108 delivery. Inadvertent mix-ups of short-acting and long-acting insulins could contribute to the risk of
1109 hypoglycemia.

1110

1111 **8.5.5 Risk of Hyperglycemia**

1112 Hyperglycemia and ketonemia could occur if insulin delivery is attenuated or suspended for an
1113 extended period. A CGM functioning poorly and significantly under-reading glucose values could
1114 lead to an inappropriate insulin recommendation. Inadvertent mix-ups of short-acting and long-acting
1115 insulins could contribute to the risk of hyperglycemia.

1116

1117 **8.5.6 Risk of Device Reuse**

1118 The study CGM system is labeled for single-patient use only. The sensor (the component of the system
1119 that enters the skin) will be single-patient use only. The transmitter and receiver may be reused during
1120 the study after cleaning the device using a hospital-approved cleaning procedure. The transmitter is

1121 attached to the sensor but does not enter the skin and the receiver is a hand held device. Subjects will
1122 be informed that FDA or relevant national authorities have approved these devices for single use and
1123 that by using them among multiple patients, bloodborne pathogens (i.e. Hepatitis B) may be spread by
1124 multiple users.

1125

1126 **8.5.7 Psychosocial Questionnaires**

1127 As part of the study, participants will complete psychosocial questionnaires which include questions
1128 about their private attitudes, feelings and behavior related to diabetes. It is possible that some people
1129 may find these questionnaires to be mildly upsetting. Similar questionnaires have been used in
1130 previous research and these types of reactions have been uncommon.

1131

1132 **8.5.8 Other Risks**

1133 Some subjects may develop skin irritation or allergic reactions to the adhesives used to secure the
1134 CGM. If these reactions occur, different adhesives or “under-taping” (such as with IV 3000,
1135 Tegaderm, etc.) will be tried, sites will be rotated frequently, and a mild topical steroid cream or other
1136 medication may be required.

1137 Whenever the skin is broken there is the possibility of an infection. The CGM sensors are inserted
1138 under the skin. It is possible that any part that is inserted under the skin may cause an infection. These
1139 occur very infrequently, but, if an infection was to occur, oral and/or topical antibiotics can be used.
1140 The risk of skin problems could be greater if you use a sensor for longer than it is supposed to be used.
1141 Therefore, participants will be carefully instructed about proper use of the sensor.

1142 Data downloaded from the CGM and blood glucose and ketone meters will be collected for the study
1143 as measures of diabetes self-management behaviors. Some people may be uncomfortable with the
1144 researchers' having such detailed information about their daily diabetes habits.

1145

1146 **8.6 Study Stopping Criteria**

1147

1148 **8.6.1 Subject Discontinuation of Study Treatment**

1149 Rules for discontinuing inControl Advice (if randomized to CGM+DSS group) or study CGM use (if
1150 randomized to the CGM group) are as follows:

- 1151 1. One episode of severe hypoglycemia, or of hyperglycemia/DKA as defined in Section 8.1
- 1152 2. One serious adverse event related to device malfunction.
- 1153 3. The subject requests that the treatment be stopped
- 1154 4. Subject pregnancy

1155

1156 **8.6.2 Criteria for Suspending/Stopping Overall Study**

1157 In the case of inControl Advice resulting in a severe hypoglycemia or severe hyperglycemia event (as
1158 defined in Section 8.1) that is thought to be advice-related (due to excess insulin administration) and
1159 occurs more than three times, the overall study will be suspended while the problem is diagnosed. The
1160 study may resume if the underlying problem can be corrected by a protocol or system modification that
1161 will not invalidate the results obtained prior to suspension. The overall study will be stopped in the
1162 event of three serious adverse events related to device malfunction.

1165 **9 MISCELLANEOUS CONSIDERATIONS**

1166 **9.1 Benefits**

1168 One purpose of this research is to reduce the frequency of hypoglycemia and severe hypoglycemic
1169 events. Hypoglycemia is the number one fear of many individuals and families with someone who has
1170 type 1 diabetes and this fear often prevents optimal glycemic control.

1171 It is expected that this protocol will yield increased knowledge about using a decision support system
1172 to help control the glucose level. In addition, it is the belief of the investigators that this study also presents
1173 prospect of direct benefit to the subjects and general benefit to others with diabetes.

1175 **9.2 Subject Compensation**

1177 Pilot subjects completing the 48-hour transitional setting admission will be compensated \$200.

1179 Subjects will be compensated \$50 for each clinic visit during the study.

1181 **9.3 Subject Withdrawal**

1182 Participation in the study is voluntary, and a subject may withdraw at any time. For subjects who
1183 withdraw, their data will be used up until the time of withdrawal.

1185 **9.4 Confidentiality**

1186 For security and confidentiality purposes, subjects will be assigned an identifier that will be used
1187 instead of their name. Protected health information gathered for this study will be shared with the third
1188 party collaborators. De-identified subject information may also be provided to research sites involved
1189 in the study.

1191 **9.5 Drug Accountability and Storage**

1192 Insulin will be provided by a third party collaborator and delivered to the Investigational Pharmacy.
1193 The clinical investigator will be responsible for maintaining adequate records of the disposition of the
1194 drug. The clinical investigator will also ensure proper security and storage of the investigational drug.

1196 Documentation: The site will document drug receipt, subject dispensing and return, returns of used and
1197 unused supplies to a third party collaborator (or on-site destruction), and will maintain a current
1198 accounting of all supplies in inventory—that is, a balance-on-hand log. The balance-on-hand, or
1199 dispensing, log will contain the protocol number, the investigative site(s), the drug name, and the
1200 medication units—such as cartridge). The site will document receipt of each drug shipment in the
1201 balance-on-hand log, noting the date, amount, and lot, batch, or ID numbers. When dispensing drug to
1202 a subject, site personnel will record the date, subject number, and amount dispensed. When a subject
1203 returns a drug, the amount used and unused will be documented, and an explanation for any
1204 inadvertent loss or destruction of supplies will also be recorded.

1205 Ensuring compliance and reconciliation: Site personnel will assess dosing regimen compliance and
1206 drug reconciliation in an ongoing manner. At each subject visit, subject compliance will be evaluated
1207 and documented, including calculating the expected amount of consumed drug given the regimen and
1208 amount of time between visits. This figure will be compared with the amount dispensed minus the
1209 amount the subject returned. Site personnel will question the subject regarding any discrepancies in
1210 these amounts and document the explanation.

1213 Insulin Storage: Insulin will be stored per product labeling as follows:

Insulin	Temperature	Use up to
In use (opened)	Room temperature: up to 86°F	28 days
Not in use (unopened)	Room temperature: up to 86°F	28 days
Not in use (unopened)	Refrigerated: 36°F to 46°F	Expiration date

1214

1215

1216

1217

1218 **10 STATISTICAL CONSIDERATIONS**

1219 The approaches to sample size and statistical analyses are summarized below. A detailed statistical
1220 analysis plan will be written and finalized prior to the completion of the study.

1224 **10.1 Sample Size**

1225 We plan on 132 subjects finishing the study, leading to a potential enrollment of 160, with up to 17.5%
1226 attrition. We base our analysis on our previous decision-support trial [7] which recruited N=120
1227 subjects and concluded with N=96 yielding effect size of 0.2 on key parameters, and on the feasibility
1228 and safety study described in the background. In this study, 11 T1DM pump users tested a prototype of
1229 the DSS leading to an estimated moderate effect size of 0.5 (Cohen D method). Assuming a substantial
1230 reduction of effect size due to (i) the focus on MDI patients, (ii) the presence of CGM in both the
1231 experimental and the control groups, and (iii) the translation of the effect to an uncontrolled
1232 environment similar to the environment of our previous trial [7], we assume a small to medium effect
1233 size. Using the statistical analysis presented below, a 0.15 effect size, with 2 groups randomized in a
1234 ratio of 2:1 (experimental-control), and 3 repeated measures (inter measure correlation of 0.5) leads to
1235 a required sample size of N=132 (expected power of 95.6%) [15].

1236 **10.2 Primary Endpoints Analyses**

1237 The primary analysis will follow the intention-to-treat principle [16]. It will include all subjects and the
1238 data will be analyzed in the group to which the subjects were assigned through randomization. Percent
1239 in range (70-180 during the day and 80-140 at night) will be computed over each month of data and
1240 entered in a Repeated Measure ANOVA, where the within-between interaction (group x period) will
1241 be studied.

1243 **10.3 Secondary Efficacy Analyses**

1244 In addition to the primary endpoint we will study:

- 1245 • HbA1c: estimated effect size of 0.15; repeated measures ANOVA, 2 groups, 2 measures,
1246 results in power of 90% with current enrollment;
- 1247 • Exposure to hypoglycemia, as measured by the percent of time spent below 70mg/dL and by
1248 the Low BG Index [13]; estimated effect size 0.25; power for repeated measures ANOVA 2x3
1249 >99%;
- 1250 • Exposure to hyperglycemia, as measured by the percent of time spent above 300mg/dL;
1251 estimated effect size 0.2; power for repeated measure ANOVA 2x3 = 99%;
- 1252 • Glucose variability as measured by the Average Daily Risk Range [14] (over 2-week period);
1253 estimated effect size 0.15; power for repeated measure ANOVA 2x6 = 95%.

1255 **10.4 Questionnaires**

1256 The following questionnaires will be completed at the randomization visit:

- 1257 • Diabetes Specific Personality Questionnaire
- 1258 • Clarke Hypoglycemia Awareness Scale [17]
- 1259 • Fear of Hypoglycemia Survey (HFS-II) [18]
- 1260 • Low Blood Sugar Survey
- 1261 • High Blood Sugar Survey
- 1262 • Diabetes Distress Scale
- 1263 • Technology Expectations Survey (CGM+DSS group)

1265
1266 The following questionnaires will be completed at the final visit at week 12:

1267 • Clarke's Hypoglycemia Awareness Scale
1268 • Fear of Hypoglycemia Survey (HFS-II)
1269 • Low Blood Sugar Survey
1270 • High Blood Sugar Survey
1271 • Diabetes Distress Scale
1272 • Technology Acceptance Survey (CGM+DSS group)

1273
1274 For each questionnaire, mean \pm SD values or percentiles appropriate to the distribution will be given
1275 by randomization group for the total score and each subscale. For questionnaires administered to both
1276 randomization groups comparisons will be made using similar ANCOVA models as described above
1277 for the primary endpoints. No formal adjustment will be made for multiple comparisons.

1278
1279 **10.5 Primary Safety Analyses**
1280 All subjects will be included in these analyses.

1281
